11.1.3. Other Variables

Discontinuations

The difference between treatments, both overall and for each primary reason, will be compared by using a 2-sided Fisher's exact test.

Confidential Page 22 of 23

Demographic and Baseline Characteristics

Comparisons between treatment groups of continuous variables will be made by using a one-way analysis of variance with treatment as a factor. For categorical variables, the Fisher's exact test will be used. All tests will be 2-sided and performed at the 0.05 level of significance.

Time-to-Event Data

Time-to-event endpoints including time-to-complete-wound-closure/healed will be evaluated using the Kaplan-Meier method. The log-rank test will be used to compare the distributions between two treatment groups.

Rate of Wound Closure, as Assessed by Computerized planimetry

Analysis of Covariance (ANCOVA) will be used to compare the rate of wound closure for the two treatment groups.

Safety Data

The primary safety endpoint for this study is any severe device-related complication where relationship to the device was assessed by the clinical event committee possible, probably, or definite. Fisher's exact test will be used to compare incidence rates of serious device-related complications as well as for any device-related complication, and for specific complications between the treatment group and the control group.

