Primary Endpoint:	The primary endpoint of this study is the incidence of complete wound closure, as assessed by the Investigator at or before Week 12 of the Treatment Phase, which is confirmed closed two weeks later. Complete wound closure is defined as complete skin re-epithelialization that is without drainage or dressing requirements
Secondary Endpoint(s):	1. The proportion of subjects in each group with complete closure of the study ulcer at or before Week 12 as assessed by computerized planimetry.

	
 2. The proportion of subjects in each group with complete wound closure of the study ulcer at or before Week 12 as assessed by independent, blinded, assessment of photographs. 3. The time to complete wound closure, as assessed by the Investigator. 4. The time to complete wound closure for all closed wounds in each group, as assessed by computerized planimetry. 5. For those wounds that have closed, the rate of wound closure for each group, as assessed by computerized planimetry. 6. Medical resource utilization associated with management of DFU and related complications as determined by a comparison of estimated costs from the presumed billing codes which would have been used for each patient.

Safety Endpoint:
	
Incidence of all investigational product, procedure, and/or wound-related adverse events or serious adverse events.

Exploratory Endpoint(s):
	
 1. The proportion of closed wounds in each group at Week 4 of the Treatment Phase 2. Co-variate analyses of the primary endpoint using those listed in section 9.3.

Description of Study Intervention(s):
	
Intervention 1: SOC therapy consisting of the use of moist wound dressings, debridement, infection surveillance and management and consistent and appropriate use of an offloading boot.
 
Intervention 2: AMNIOEXCEL Plus used in conjunction with SOC therapy.
 
Intervention 3: Apligraf used in conjunction with SOC therapy.

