3 OBJECTIVES AND ENDPOINTS

Table 3: Objectives and Endpoints

OBJECTIVES	ENDPOINTS
Primary	
The primary objective of this study is to compare outcomes associated with the use of AMNIOEXCEL Plus Placental Allograft Membrane, Apligraf living, bi-layered skin substitute and SOC in the management of DFUs.	The primary endpoint of this study is the incidence of complete wound closure, as assessed by the Investigator at or before Week 12 of the Treatment Phase and confirmed 2 weeks later. Confirmed complete wound closure is defined as complete skin re-epithelialization that is without drainage or dressing requirements.
Secondary	
1. Determine the proportion of subjects in each study arm with complete closure of the study ulcer at or before 12 weeks of treatment	1. Proportion of subjects with complete closure of the study ulcer at or before Week 12 and confirmed 2 weeks later as assessed by computerized planimetry. 2. Proportion of subjects with complete wound closure of the study ulcer at or before Week 12 and confirmed 2 weeks later as assessed by independent, blinded, assessment of photographs.
2. Determine the time to complete wound closure in each study arm	1. Time to complete wound closure, as assessed by the Investigator. 2. Time to complete wound closure, as assessed by computerized planimetry.
3. Determine the rate of wound closure in each study arm	1. Rate of wound closure, as assessed by computerized planimetry.
4. Assess medical resource utilization outcomes in each study arm	1. Medical resource utilization associated with treatment of DFU and related complications as determined by a comparison of estimated costs from the presumed billing codes which would have been used for each patient.
Exploratory	
1. The proportion of subjects in each cohort whose wounds are closed at 4 weeks of treatment.	1. Wound closure status at Week 4 of Treatment
2. The effect of any covariate on the primary endpoint.	1. Co-variate analyses of the primary endpoint using those listed in section 9.3.
Safety Endpoints	
The safety objective of this study is to assess adverse events associated with either of the study treatments and/or all study procedures in the management of DFUs.	Incidence of all treatment, procedure, and/or wound-related adverse events or serious adverse events in any of the study cohorts.

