9.4.7 SAFETY ANALYSES

AEs/SAEs related to the investigational product, study ulcer and/or study procedures and will be recorded.

AEs will be coded according to the most recent version of the Medical Dictionary for Regulatory Activities (MedDRA) AE coding dictionary, and grouped by body system. The number and percentage of subjects experiencing at least one AE of any type, AEs within each body system and AEs within each preferred term will be presented for each treatment group. Separate summaries will be provided for all AEs, device related AEs, SAEs and AEs leading to withdrawal.

All safety parameters will be summarized descriptively by treatment assignment. No inferential statistics are planned.

Listings of complications will be presented, include complication type, relation to study device, relation to procedure, action taken, and clinical outcome. Separate listings will be constructed for complications with possible, probable, or definite relationship to the device, serious complications, and for all complications. The listing for all complications will be sorted by complication type.

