2.4. Safety Endpoints

The safety objective of this study is to assess adverse events associated with either of the study treatments and/or all study procedures in the management of DFUs.

Confidential Page 7 of 23

3. Study Design

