10.6. Safety Analysis

Safety will be assessed through reports of adverse events and serious adverse events. Adverse Events related to the device, study ulcer and/or study procedures and all Serious Adverse Events will be recorded.

All safety parameters will be summarized descriptively by treatment. No inferential statistics are planned.

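### The Safety Data paragraph in SAP 11.1.3 orders Fisher tests on a primary safety endpoint and an event committee that the rest of the plan does not contain, while SAP 10.6 and the protocol plan no safety inference

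*SAP*

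**What the plan says.** Under Safety Data, SAP 11.1.3 states: "The primary safety endpoint for this study is any severe device-related complication where relationship to the device was assessed by the clinical event committee", with relatedness graded possible, probable or definite. It continues that Fisher's "exact test will be used to compare incidence rates of serious device-related complications as well as for any device-related complication", and also "for specific complications between the treatment group and the control group".

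The rest of the plan reads differently:

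- SAP 10.6: "All safety parameters will be summarized descriptively by treatment. No inferential statistics are planned".
- Protocol 9.4.7: "All safety parameters will be summarized descriptively by treatment assignment. No inferential statistics are planned". The Safety Assessment text in the synopsis says the same.
- The safety endpoint in the synopsis is "Incidence of all investigational product, procedure, and/or wound-related adverse events or serious adverse events". In Protocol section 3 it is "Incidence of all treatment, procedure, and/or wound-related adverse events or serious adverse events in any of the study cohorts". Neither place calls a safety endpoint primary.
- SAP 2.4 keeps the protocol's objective, to "assess adverse events associated with either of the study treatments and/or all study procedures".

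SAP 10.7 adds that groups will be compared on adverse-event incidence, without saying whether this is descriptive. It also gives two accounts of a treatment-emergent event.

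**The concern.** Both instructions are current SAP text, and nothing says which prevails. An analyst who follows SAP 10.6 reports no safety p-values. One who follows 11.1.3 reports several, on an endpoint that is labelled primary but absent from the protocol's endpoint list, judged by a body that the plan does not set up, between two groups that are not identified.

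SAP section 5 says the study is not adequately powered for hypothesis testing. A non-significant safety test could therefore be read as reassurance that it does not give. A significant one on device-related events could partly reflect how the events are defined.

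**Working it through.** The plan states no figure for safety, so there is none to reproduce. The main check is to set the passages side by side.

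1. **Inference.** SAP 11.1.3 orders Fisher tests on serious device-related, any device-related and specific complications. SAP 10.6, Protocol 9.4.7 and the synopsis rule out inferential safety statistics. These cannot all be followed.
2. **Endpoint.** SAP 11.1.3 restricts to severe, device-related events and calls them primary. The protocol's endpoint covers AEs and SAEs related to product or treatment, procedure or wound. Protocol 9.4.7 does plan a summary of device-related AEs and listings of device-related and serious complications, but all of this is descriptive.
3. **Adjudicator.** The clinical event committee appears only in SAP 11.1.3. Protocol 8.3.9 has the Investigator assess the relatedness of SAEs, and Protocol 8.2 has the sites decide how much to record for an AE according to its relatedness. Protocol 10.1.5 puts safety oversight with the Medical Monitor.
4. **Severe or serious.** The endpoint uses severe events and the first test uses serious ones. Protocol 8.3.6.1 defines severe as a grade of intensity. Protocol 8.3.5 defines serious by outcome. The two sets differ.
5. **Groups.** There are three arms, randomized 1:1:1 (SAP 3.1). Protocol 9.4.5 has two active groups and one control, SOC alone. A single treatment group could be either allograft or both pooled.
6. **Record of change.** SAP section 12 lists the photograph review and Week 4 closure status, and nothing on safety.

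**Conditional check on the device-related tests.** Suppose 'device' means the investigational product, which Protocol 8.3.2 limits to the two allografts. Suppose also that 'control' means SOC alone, as in Protocol 9.4.5. Protocol 8.3.3 classes SOC materials and sharp debridement as study procedure, so an SOC subject could not have a device-related event.

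Inputs: 38 per cohort (SAP section 5); two-sided 0.05 (SAP 10.1); a safety population of all subjects who received their allocated treatment (SAP 8.3), so no attrition is taken off; SOC count 0.

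One allograft arm against SOC, with x events against 0, gives two-sided p = 2 × C(38,x) / C(76,x):

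- x = 5: 2 × 501,942 / 18,474,840 = 0.054
- x = 6: 2 × 2,760,681 / 218,618,940 = 0.025

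So p<0.05 first occurs at 6/38 (15.8%). With both allografts pooled (76 against 38), summing the tables no more probable than the one observed gives 0.0504 at 8/76 and 0.028 at 9/76. The threshold is then 9/76 (11.8%).

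The documents give no related-event rate. At assumed true allograft rates, the binomial chance of reaching each threshold is:

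| Assumed rate | 6 or more of 38 | 9 or more of 76 |
|---|---|---|
| 5% | 1.1% | 1.3% |
| 10% | 17.5% | 34.9% |
| 15% | 51.5% | 82.3% |
| 20% | 80.0% | 97.8% |

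On this reading the p-value depends only on the allograft count. It carries no information about complications under SOC.

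**SAP 10.7.** One definition of a treatment-emergent event starts at the first randomized treatment. The other relies on an active phase bounded by the first and last dose of test article, a term that does not fit the SOC arm well. Protocol 8.3.1 already gives a window that works for every arm: onset or worsening after the first randomized treatment, up to the subject's exit.

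**The case against.** The strongest reply is that SAP 11.1.3 is a stray paragraph. Three other places say that safety is descriptive, a sensible analyst would follow them, and Protocol 9.4.7 itself reports device-related and serious complications. The last part stands: device-related reporting as such is not new. What is new is the primary label, the restriction to severe events, the committee and the tests. The first part does not settle the matter, because the paragraph is specific, current and nowhere overridden.

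A reader might infer that the comparison with SOC is a structural zero as a matter of fact. The documents do not establish that. SAP 11.1.3 defines neither 'device' nor 'control group'. Protocol 2.2 describes Apligraf as registered as a medical device, the eligibility criteria call the boot an offloading device, and Protocol 8.3.6.2 allows relatedness to the comparator. If the boot counted as a device, SOC subjects could have device-related events. If control meant Apligraf, the zero would not arise. Nor does the wording clearly tie the test of specific complications to device-relatedness, so the zero need not reach it.

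A reader might also infer that the tests are likely to produce a false safety signal. The figures do not support that: at an assumed 5% rate, rejection is about 1%.

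**Conclusion.** The contradiction holds as written and needs no assumption. SAP 11.1.3 conflicts with SAP 10.6, Protocol 9.4.7 and the synopsis on inference, with the protocol's endpoint list on what is measured, and with Protocol 8.3.9 and 10.1.5 on who judges and oversees. It is also inconsistent within itself on severe and serious events, and it does not fit a three-arm trial. The consequence is a safety report that the SAP does not determine; the primary efficacy analysis is unaffected.

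The statement that the device-related tests against SOC would not measure a difference in complications is conditional on 'device' meaning the allografts and 'control' meaning SOC alone. The thresholds of 6/38 and 9/76 illustrate that case at full enrolment. The event rates in the table are assumptions and forecast nothing.

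**What to change.** Replace the Safety Data paragraph of SAP 11.1.3 with the protocol's safety endpoint, Investigator-assessed relatedness and descriptive summaries for each of the three arms. Delete the committee reference and the Fisher tests. Write 'investigational-product-related' in place of 'device-related', and report procedure- and wound-related events for all arms beside it. Show SOC events as the sites recorded them, without a footnote declaring them zero by definition, since that would write one reading of 'device' into the tables.

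In SAP 10.7, state that the comparison of groups is descriptive. Use one treatment-emergent definition for all arms, matching Protocol 8.3.1, including worsening and the end at study exit.

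If a committee did adjudicate events, define instead the endpoint, the adjudicator, 'device' and the groups compared, and record this as a change in SAP section 12.

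Restoring the protocol's plan costs SAP wording and table shells only. It needs no new data.

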12. CHANGE FROM PLANNED ANALYSIS

Independent photograph review data analysis

The independent photograph review was done by three independent investigators, the data has been collected and evaluated. However, due to the flawed methodology of data assessment, the data is not going to be analyzed and will not be presented in CSR

Wound closure status at Week 4

Wound closure status at Week 4 is determined as the wound closure by investigator assessment, and is not be confirmed by the 2-week follow-up visit.

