6.3 MEASURES TO MINIMIZE BIAS: RANDOMIZATION AND BLINDING

This study will use randomization to minimize bias in this open label study. Randomization will occur in a 1:1:1 ratio and use a mixed block methodology. No blinding is possible. As well, no analytical blinding will occur during data review and/or analysis.

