Randomization will be used to minimize bias in this open label study. Randomization will occur in a 1:1:1 ratio and use a mixed block methodology. No blinding is possible. As well, no analytical blinding will occur during data review and/or analysis.

7. Interim Analysis

An interim analysis will occur after 50% of subjects have met the primary endpoint of the study. Descriptive statistics will be provided. Primary and secondary endpoints will be evaluated at the time of interim analysis. There is no hypothesis testing for the interim analysis, and thus no alpha allocation is considered.

8. Analysis Populations

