9.1. Primary Endpoint Analysis

The primary endpoint of this study is the incidence of complete wound closure, as assessed by the Investigator at or before Week 12 of the Treatment Phase and confirmed closed 2 weeks later. Confirmed complete wound closure is defined as complete skin re-epithelialization that is without drainage or dressing requirements two weeks later.

Confidential Page 13 of 23

A subject is considered to have a closed wound (i.e., a closure success) if the subject's treated wound closes between week 1 and 12 and is noted by the site as closed on both follow-up visits.

A subject is considered to not have a closed wound (i.e., a closure failure) if they meet any of the following:

- the subject's treated wound does not close by week 12
- the subject's treated wound closes between week 1 and 12 and is noted as open on either or both of the follow-up visits.

A subject is considered to have an undetermined wound closure if the subject's treated wound closes between week 1 and 12 and the subject misses either or both of the follow-up visits. These subjects may become part of extended analyses.

The primary analysis will be conducted on the ITT population. The proportion of subjects with confirmed closed study wound, as assessed by the investigator, will be compared between AMNIOEXCEL Plus and Apligraf, and AMNIOEXCEL Plus and SOC. The proportion of subjects with confirmed complete wound closure will be compared using the Cochran–Mantel–Haenszel (CMH) test and logistic regression.

For the primary efficacy analysis, missing values will be imputed using last observation carried forward (LOCF). The differences in confirmed complete wound closure rate between treatment arms will be summarized along with 95% confidence intervals.

A point estimate of the incidence will be presented along with its associated exact 95% confidence interval based on the binomial distribution for Active Treatment and Control Treatment patients respectively.

The complete wound closure as assessed by the Investigator at the end of the Treatment Phase will be listed for each patient.

In addition, subgroup analyses of the primary endpoint will be performed for age, sex, race, region, and other groupings if appropriate.

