9.2. Secondary Endpoint Analysis

The secondary endpoints that will be analyzed as part of this trial are as follows:

• Proportion of subjects with complete closure of the study ulcer at or before Week 12 and confirmed 2 weeks later as assessed by computerized planimetry.

Confidential Page 14 of 23

- Proportion of subjects with complete wound closure of the study ulcer at or before Week 12 and confirmed 2 weeks later as assessed by independent, blinded, assessment of photographs.
- The Time to complete wound closure, as assessed by the Investigator.
- The Time to complete wound closure, as assessed by computerized planimetry.
- For those wounds that have closed, the rate of wound closure for each group, as assessed by computerized planimetry.
- Medical resource utilization associated with management of DFU and related complications as determined by a comparison of estimated costs from the presumed billing codes which would have been used for each patient. The summary will be provided by an independent group, results will not be included in this analysis

Proportion of ulcers with complete wound closure during the treatment phase as assessed by planimetry will be compared using Logistic Regression with specified baseline covariates in the model.

Time to complete wound closure will be analyzed using the Log-rank test or Cox Proportional Regression Model. The Kaplan-Meier methods will be used to present the distribution of time to complete wound closure.

Summary statistics will be provided for the rate of wound closure for the two treatment groups.

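### SAP Section 12 drops the only endpoint described as blinded after the reads were evaluated and does not state the flaw, so selective reporting cannot be excluded

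*SAP*

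**What the plan says.** The primary endpoint is complete closure "as assessed by the Investigator at or before Week 12 of the Treatment Phase and confirmed closed 2 weeks later" (SAP 9.1; Protocol 9.1 agrees). Protocol 6.3 describes the trial as open label and adds: "No blinding is possible. As well, no analytical blinding will occur during data review and/or analysis". SAP Section 6 repeats this.

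The protocol synopsis, Protocol Table 3, Protocol 9.1 and SAP 9.2 all include a secondary endpoint of closure "as assessed by independent, blinded, assessment of photographs". SAP 9.2 introduces its list with "The secondary endpoints that will be analyzed as part of this trial are as follows".

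SAP Section 12 states that three independent investigators carried out the photograph review and that "the data has been collected and evaluated". It then says that, "due to the flawed methodology of data assessment, the data is not going to be analyzed and will not be presented in CSR".

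Planimetric closure stays in the plan as a separate secondary endpoint (SAP 9.2).

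**The concern.** An Investigator who knows the allocated product also decides whether the wound has closed. Closure involves judgement, so knowing the product can influence the call. A blinded read of photographs is the usual safeguard, and here it was planned, carried out and then withdrawn.

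The order of events matters. If a planned endpoint is set aside before anyone has looked at it, for a stated defect, the decision can be assessed on its merits. If it is set aside after evaluation, for an unstated defect, in a study without analytical blinding, a reader cannot tell a sound exclusion from a selective one. Keeping the data out of the CSR also removes the material needed to find out.

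**Working it through.** No figure in the plan addresses this point. The check is mainly a comparison of the text, with a short calculation for scale.

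**1. Who assesses closure, and is the assessor masked?**

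| Measure | Source | Assessor | Masking | Status |
|---|---|---|---|---|
| Investigator closure (primary) | Protocol 9.1, SAP 9.1 | Site Investigator | None; open label | Analysed |
| Planimetric closure | Protocol 8.2 (Photography), SAP 9.2 | Software area from site images | Not described | Analysed |
| Photograph review | Protocol Table 3 and 9.1, SAP 9.2 | Three independent readers (SAP 12) | Endpoint described as blinded | Dropped (SAP 12) |

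Once the third row is removed, no measure described as blinded remains.

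**2. SAP 9.2 against SAP 12.** SAP 9.2 lists the photograph endpoint for analysis; Section 12 says it will not be analysed. In the same list, SAP 9.2 notes that the resource-use results fall outside this analysis. The photograph endpoint carries no such note.

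**3. What Section 12 leaves open.** It gives a category of reason but not the defect, its date, who decided or what they could see. No re-read or replacement masked assessment is offered.

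**4. Could results by arm have been seen?** The sponsor's Statistical and Data Management teams hold the randomization code (Protocol 10.1.8.1, SAP 6). Secondary endpoints were to be evaluated at the interim analysis (Protocol 9.4.8, SAP 7). There is no analytical blinding. Nothing in the plan prevented access to photograph results by arm, and nothing says that such access occurred.

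**5. Scale.** The inputs are 38 subjects per arm, an assumed 90% closure rate and a stated half-width of 13.5 points (Protocol 9.2, SAP 5).
- Half-width for one rate: 1.96 × √(0.9 × 0.1 / 38) = 0.095.
- Half-width for a difference between two arms: 1.96 × √(2 × 0.9 × 0.1 / 38) = 0.135. The stated 13.5 points therefore matches a between-arm difference, although the text attaches it to the closure rate. It is used here only as a yardstick for a difference.
- One reclassified subject: 1/38 = 2.6 points. Five net calls in one direction: 5/38 = 13.2 points, close to the half-width.
- Cochran–Mantel–Haenszel (CMH) test with one stratum (an assumption), 38 per arm and equal true closure in both arms: statistic = (75/76) × Pearson χ², critical value 3.84.

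| True closed per arm (assumed) | Over-calls in one arm needed for p < 0.05 | Share of truly open wounds in that arm |
|---|---|---|
| 12, 15 or 19 of 38 | 9 | 35%, 39%, 47% |
| 23 of 38 | 8 | 53% |
| 27 of 38 | 7 | 64% |
| 30 of 38 | 6 | 75% |

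A few one-sided calls shift the estimate visibly. Producing a significant result from no true difference would need much larger one-sided error. The documents do not indicate how much miscalling there was.

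**The case against.** **Planimetry remains.** This stands in part. The app measures area automatically and the site does not enter it (Protocol 8.2). SAP 9.2 compares planimetric closure by logistic regression, and Equation 4b requires two successive zero readings. It would be wrong to call the photograph review the trial's only protection. However, unmasked site staff take the images, after any debridement they perform, and no section describes planimetry as masked. It also yields an area, whereas the primary definition adds absence of drainage and of any need for a dressing.

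**The photograph read was never a full check.** This also stands. Photographs are taken after dressing removal and cleansing, so drainage and dressing need are hard to judge from them. Losing the reads weakens the check on the primary result but does not make that result uninterpretable.

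**The change is disclosed.** Section 12 exists to record departures and may explain why SAP 9.2 was left as it was. But it discloses that the endpoint was dropped, not the defect that would justify dropping it.

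**Flawed data should not be reported.** Tabulating flawed reads does not restore a masked comparison. The fix claims no reliability for them; it lets a reader see what was set aside and why.

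**The stakes are limited.** Protocol 9.4.6 labels the secondary analyses exploratory, SAP 5 says the study is not powered for hypothesis testing, and the primary analysis is unchanged. This tempers the weight of the point but does not answer it.

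**A stronger reading.** A reader might infer that the endpoint was suppressed because of its results, by people who had seen them by arm. The documents do not support that. Section 12 gives a methodological reason. Its statement that the data were evaluated may mean only that the readers scored the images or that quality was reviewed. No section says who decided or with what access.

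**Conclusion.** The concern holds as a risk that cannot be excluded, not as a demonstrated fault. A planned, collected and evaluated secondary endpoint, the only one described as blinded, is barred from analysis and from the CSR for an unspecified flaw, and SAP 9.2 and Section 12 disagree about it. This is more than missing detail, because Section 12 sets a rule of non-reporting.

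No bias in the primary result has been measured. The 2.6 points per reclassified subject and the 6 to 9 one-sided over-calls indicate scale only. They assume the planned 38 per arm; the over-call figures also assume equal true closure of about 32% to 79% and an unstratified test. Planimetric closure remains as a partly objective non-Investigator check.

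**What to change.** Change SAP Section 12 so that the CSR:

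- states the methodological flaw, when it was found, who decided to drop the endpoint, and whether they had access to results by arm;
- lists the existing reader calls by subject;
- gives between-reader agreement, agreement with the Investigator, and closure by arm, clearly labelled non-confirmatory;
- shows planimetric closure alongside as the remaining non-Investigator check.

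Add a cross-reference at the photograph endpoint in SAP 9.2 to Section 12, so that the two sections agree.

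The cost is a short explanation, a listing and a summary table, provided that the subject-level calls of each reader are retrievable; the SAP says the data were collected but not in what form. The downside is that a summary of limited reliability appears in the CSR with a caveat. It does not replace a valid masked assessment. Whether a masked re-read would be worthwhile cannot be judged until the flaw is described.
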